11.10.1 Specific Guidance for Cytokine Release Syndrome

Cytokine release syndrome (CRS) is clinically defined and may have various manifestations. There are no established diagnostic criteria. Signs and symptoms of CRS may include:

- constitutional: fever, rigors, fatigue, malaise
- neurologic: headache, mental status changes, dysphasia, tremors, dysmetria, gait abnormalities, seizure
- respiratory: dyspnea, tachypnea, hypoxemia
- cardiovascular: tachycardia, hypotension
- gastrointestinal (GI): nausea, vomiting, transaminitis, hyperbilirubinemia
- hematology: bleeding, hypofibrinogenemia, elevated D-dimer
- skin: rash

Subjects may be at an increased risk for CRS during the first few days following administration of protocol-required therapies. CRS may be life threatening or fatal. Infusion reactions may be clinically indistinguishable from manifestations of CRS. Throughout the treatment with protocol-required therapies, monitor subjects for clinical signs (eg, fever, tachycardia, dyspnea, tremors) and laboratory changes (eg, transaminase increase) which may be related to CRS.

Refer to the main protocol body for the more information on the following:

- grading and management of CRS (based on the adopted grading system referenced in Lee et al, 2014) should be performed according to the guidelines provided
- general guidance for re-start of infusion after interruptions/delay/withholding and dose modifications.
- dose-limiting toxicity (DLT) considerations for grade 3 and 4 CRS

Fever reported outside the context of CRS will be graded per Common Toxicology Criteria for Adverse Events (CTCAE) version 5.0.

11.10.2 Cairo-Bishop Clinical Tumor Lysis Syndrome Definition and Grading

Common Terminology Criteria for Adverse Events (CTCAE) version 5.0 classifies tumor lysis syndrome (TLS) in grade 3 (present), grade 4 (life threatening consequences; urgent intervention indicated) and grade 5 (death). Presence of TLS is not clearly defined by CTCAE version 5.0. Cairo and Bishop developed a system for defining and grading TLS based on Hande-Garrow classification of laboratory or clinical TLS (Coiffier et al, 2008). For this trial, the Cairo-Bishop classification will be used to define presence of TLS, ie, presence of laboratory TLS (see [Table 11-4](#)) and clinical TLS (see [Table 11-5](#)) including grading.

Based on the Cairo and Bishop system, laboratory TLS is defined as any 2 or more abnormal serum values present within 3 days before or 7 days after initiation of treatment in the setting of adequate hydration (with or without alkalinization) and use of a hypouricemic agent ([Table 11-4](#)).

Table 11-4. Cairo-Bishop Definition of Laboratory Tumor Lysis Syndrome

Element	Value	Change from Baseline
Uric acid	$\geq 476 \mu\text{mol/L}$ or 8 mg/dL	25% increase
Potassium	$\geq 6.0 \text{ mmol/L}$ or 6 mg/L	25% increase
Phosphorus	$\geq 2.1 \text{ mmol/L}$ for children or $\geq 1.45 \text{ mol/L}$ for adults	25% increase
Calcium	$\leq 1.75 \text{ mmol/L}$	25% decrease

Note: Two or more laboratory changes within 3 days before or 7 days after cytotoxic therapy will constitute laboratory tumor lysis syndrome.

Clinical TLS requires the presence of laboratory TLS in addition to 1 or more of the following significant complications: renal insufficiency, cardiac arrhythmias/sudden death, and seizures ([Table 11-5](#)). The grade of clinical TLS is defined by the maximal grade of the clinical manifestations as detailed in [Table 11-5](#).

Table 11-5. Cairo-Bishop Clinical Tumor Lysis Syndrome Definition and Grading

Grade	Creatinine ^{a,b}	Cardiac Arrhythmia ^a	Seizure ^a
0	≤ 1.5 x ULN	None	None
1	1.5 x ULN	Intervention not indicated	--
2	> 1.5 – 3.0 x ULN	Non-urgent medical intervention indicated	One brief, generalized seizure; seizure(s) well controlled by anticonvulsants or infrequent focal motor seizures not interfering with ADL
3	> 3.0 – 6.0 x ULN	Symptomatic and incompletely controlled medically or controlled with device (eg, defibrillator)	Seizure in which consciousness is altered; poorly controlled seizure disorder; with breakthrough generalized seizures despite medical intervention
4	> 6.0 x ULN	Life-threatening (eg, arrhythmia associated with CHF, hypotension, syncope, shock)	Seizure of any kind which are prolonged, repetitive or difficult to control (eg, status epilepticus, intractable epilepsy)
5	Death	Death	Death

Note. Laboratory TLS and at least 1 clinical complication will constitute clinical TLS.

ADL = activities of daily living; CHF = congestive heart failure; TLS = tumor lysis syndrome; ULN = upper limit of normal

^a Not directly or probably attributable to therapeutic agent.

^b If no institutional ULN is specified, age/sex ULN creatinine may be defined as follows: > 1 to < 12 years of age, both male and female, 61.6 μmol/L; ≥ 12 to < 16 years, both male and female, 88 μmol/L; ≥ 16 years, female 105.6 μmol/L, male 114.4 μmol/L.

11.10.3 Specific Guidance for Immune-effector Cell-associated Neurologic Syndrome

For this trial, immune-effector cell associated neurologic syndrome (ICANS) will be using the criteria referenced in the publication by Lee et al (2019). While the grading system has been developed in large part from chimeric antigen receptor T cells (CAR-T) therapies, symptoms of ICANS may be shared among immune effector-cell associated therapies such as bispecific T-cell engager (BiTE) molecules. Although there may be a wide range of symptoms associated with ICANS, subjects may have a stereotypic course of a specific set of symptoms. The earliest manifestations of ICANS are tremor, dysgraphia, mild difficulty with expressive speech (especially in naming objects), impaired attention, apraxia, and mild lethargy.

ICANS grade is determined by the most severe event (eg, depressed level of consciousness, seizure, motor findings, raised intracranial pressure [ICP]/cerebral edema) not attributable to any other cause. Refer to the immune effector cell-associated encephalopathy (ICE) score below for grading of ICANS.

Immune Effector Cell-associated Encephalopathy (ICE) Assessment Tool

- Orientation: Orientation to year, month, city, hospital: 4 points
- Naming: ability to name 3 objects (eg, point to clock, pen, button): 3 points
- Following commands: ability to follow simple commands (eg, “Show me two fingers” or “Close your eyes and stick out your tongue”): 1 point
- Writing: ability to write a standard sentence (eg, “Our national bird is the bald eagle”): 1 point
- Attention: ability to count backwards from 100 by 10: 1 point

ICE scoring

- 7-9, grade 1
- 3-6, grade 2
- 0-2, grade 3
- 0 due to subject unarousable and unable to perform ICE
- Assessment, grade 4

Table 11-6. ASBMT Immune Effector Cell-associated Neurotoxicity Syndrome (ICANS) Consensus Grading for Adults

Neurotoxicity Domain ^a	Grade 1	Grade 2	Grade 3	Grade 4
ICE score ^b	7-9	3-6	0-2	0 (subject is unarousable and unable and unable to perform ICE)
Depression level of consciousness ^c	Awakens spontaneously	Awakens to voice	Awakens only to tactile stimulus	Subject is unarousable or requires vigorous or repetitive tactile stimuli to arouse. Stupor or coma
Seizure	N/A	N/A	Any clinical seizure focal or generalized that resolves rapidly or nonconvulsive seizures on EEG that resolve with intervention	Life-threatening prolonged seizure (> 5 min); or repetitive clinical or electrical seizures without return to baseline in between
Motor findings	N/A	N/A	N/A	Deep focal motor weakness such as hemiparesis or paraparesis
Elevated ICP/cerebral edema	N/A	N/A	Focal/local edema on neuroimaging ^d	Diffuse cerebral edema on neuroimaging; Decerebrate or decorticate posturing; or Cranial nerve VI palsy; or Papilledema; or Cushing's triad

ASBMT = American Society for Blood and Marrow Transplantation; CTCAE = Common Terminology Criteria for Adverse Events; EEG = electroencephalogram; ICANS = immune-effector cell associated neurologic syndrome; ICE = immune effector cell-associated encephalopathy; ICP = intracranial pressure; N/A = not applicable.

^a Other signs and symptoms such as headache, tremor, myoclonus, asterixis, and hallucinations may occur and could be attributable to immune effector-cell engaging therapies. Although they are not included in this grading scale, careful attention and directed therapy may be warranted.

^b A subject with an ICE score of 0 may be classified as grade 3 ICANS if awake with global aphasia, but a subject with an ICE score of 0 may be classified as grade 4 ICANS if unarousable.

^c Depressed level of consciousness should be attributable to no other cause (eg, no sedating medication).

^d Intracranial haemorrhage with or without associated edema is not considered a neurotoxicity feature and is excluded from ICANS grading. It may be graded according to CTCAE v5.0.

Source: Lee et al, 2019

Assessment and Supportive Care Recommendations (all grades)

- Neurologic assessment and grading at least twice a day to include cognitive assessment and motor weakness
- MRI of the brain with and without contrast (or brain computed tomography (CT) if MRI is not feasible) for ≥ grade 2 neurotoxicity
- Neurology consultation at first sign of neurotoxicity

- Conduct electroencephalogram (EEG) for seizure activity for \geq grade 2 neurotoxicity
- Aspiration precautions; IV hydration
- Use caution when prescribing medications that can cause central nervous system (CNS) depression (aside from those needed for seizure prophylaxis/treatment)

Table 11-7. Assessment and Supportive Care Recommendations

Treatment by Grade	No Concurrent CRS	Additional Therapy if Concurrent CRS
Grade 1	
 • Supportive care 	In the setting of grade \geq 3 CRS with hypotension, tocilizumab ^{e,f} 8 mg/kg IV over 1 h (not to exceed 800 mg/dose) ^d
Grade 2 ^c	
 • Supportive care • Dexamethasone 10 mg IV x 1. Can repeat every 6 hours or methylprednisolone 1 mg/kg IV every 12 h if symptoms worsen. 	Anti-IL-6 therapy as per grade 1 ^d Consider transferring subject to ICU if neurotoxicity associated with grade \geq 2 CRS
Grade 3 ^c	
 • Supportive care • Dexamethasone 10 mg IV every 6 h or methylprednisolone, 1 mg/kg IV every 12 h^a • Consider repeat neuroimaging (CT or MRI) every 2-3 days if subject had persistent grade \geq 3 neurotoxicity. 	Anti-IL-6 therapy as per grade 1 ^d
Grade 4 ^c	
 • ICU care, consider mechanical ventilation for airway protection. • High-dose corticosteroids ^{a,b} • Consider repeat neuroimaging (CT or MRI) every 2-3 days if subject has persistent grade \geq 3 neurotoxicity. • Treat convulsive status epilepticus per institutional guidelines. 	Anti-IL-6 therapy as per grade 1 ^d

CRS = cytokine release syndrome; CT = computed tomography; ICU = intensive care unit; IL-6 = interleukin-6; IV = intravenous; MRI = magnetic resonance imaging; PK = pharmacokinetics.

^a Antifungal prophylaxis should be strongly considered in subjects receiving steroids for the treatment of CRS and/or neurotoxicity.

^b For example, methylprednisolone IV 1000 mg/day for 3 days, followed by rapid taper at 250 mg every 12 hours for 2 days, and 60 mg every 12 hours for 2 days.

^c Diagnostic lumbar puncture for grade 3-4 neurotoxicity; consider for grade 2.

^d Repeat tocilizumab every 8 hours as needed if not responsive to IV fluids or increasing supplemental oxygen. Limit to a maximum of 3 doses in a 24-hour period; maximum total of 4 doses.

^e If tocilizumab is not available, siltuximab (an anti-IL-6 monoclonal antibody) may be used in the management of cytokine release syndrome, following the criteria outlined in the Management of Adverse Events table. The recommended dose of siltuximab is 11 mg/kg administered over 1 hour as an intravenous infusion, consistent with the prescribing information for the treatment of multicentric Castlemans disease (Sylvant Prescribing Information), and the CARTOX Working Group Guidelines for CRS management (Neelapu, 2018). Siltuximab may be repeated if needed, in the event that CRS recurs after a subsequent infusion of AMG 160. Siltuximab may not be repeated in an individual subject that develops anaphylaxis to siltuximab, or gastrointestinal perforation after siltuximab.

^f A subgroup analysis for subjects treated with siltuximab will be evaluated, including CRS outcomes, safety, and PK data.

11.11 **Appendix 11. Performance Status According to Eastern Cooperative Oncology Group (ECOG)**

ECOG Performance Status Scale	
Grade	Descriptions
0	Fully active, able to carry on all pre-disease performance without restriction
1	Restricted in physically strenuous activity but ambulatory and able to carry out work of a light or sedentary nature, eg, light house work, office work
2	Ambulatory and capable of all selfcare but unable to carry out any work activities. Up and about more than 50% of waking hours
3	Capable of only limited selfcare, confined to bed or chair more than 50% of waking hours
4	Completely disabled. Cannot carry on any selfcare. Totally confined to bed or chair
5	Dead

ECOG = Eastern Cooperative Oncology Group.

Source: Oken et al, 1982

11.12 Appendix 12. Response Evaluation Criteria in Solid Tumors Version 1.1 (modified RECIST 1.1)

Response Evaluation Criteria in Solid Tumors version 1.1 (RECIST 1.1) are guidelines for assessing tumor burden changes in response to treatment (Eisenhauer et al, 2009). Additional patterns of response have been observed with immune-enhancing therapies, including delayed clinical response, leading to criteria modifications to capture treatment responses more accurately (Wolchok JD et al, 2009; Nishino M et al, 2013). This study utilizes modified RECIST 1.1 criteria which applies aspects of the immune-related response criteria (including requiring confirmation of disease progression) to RECIST 1.1 as outlined below.

Modified RECIST 1.1 tumor response assessment

- All measurable and non-measurable lesions should be assessed at screening, all defined tumor assessment time points (Schedule of Assessment), and any unscheduled imaging visits.

Measurable lesions:

- Non-nodal lesions with clear borders that can be measured accurately and serially in one dimension in the axial plane (longest diameter \geq 10 mm measured by MRI/CT with scan slice thickness \leq 5 mm).
- Nodal lesions with the longest diameter perpendicular to the long axis (short axis) \geq 15 mm on MRI/CT.
- Must exclude simple cysts, pleural/pericardial effusions and ascites.

Non-measurable lesions:

- All other lesions, including small lesions (longest diameter $<$ 10 mm or pathological lymph nodes with \geq 10 mm but $<$ 15 mm short axis) are considered non-measurable and characterized as non-**target** lesions.
- Other examples of non-measurable lesions include:
 - Lesions with prior local treatment:
 - Tumor lesions situated in a previously irradiated area, or an area subject to other loco-regional therapy, should not be considered measurable unless there has been demonstrated progression in the lesion.
 - Biopsied lesions
 - Categorically, clusters of small lesions, bone lesions, inflammatory breast disease, and leptomeningeal disease are non-measurable. See Imaging Procedural Manual provided by the central imaging core laboratory for additional guidance.

Target lesions and measurable tumor burden:

- **Target** lesions:
 - Measurable lesions (≤ 5 lesions per organ, ≤ 10 total) selected at baseline on the basis of
 - Size and suitability for accurate repeated measurements by imaging.
 - Representative of the subject's tumor burden, all organs involved and overall disease status

Non-target lesions:

- All measurable lesions not selected as **target** lesions and non-measurable lesions
- Non **target** lesions will be qualitatively evaluated
 - Values: 'Present', 'absent' or 'unequivocal progression'.
- Other definitions
 - Unable to evaluate (UE): Any lesion present at baseline which was not assessed or was unable to be evaluated leading to an inability to determine the status of that particular tumor for that time point
 - Not Available (NA): Scan not available
 - Not Done (ND): Radiologic imaging was not performed at this time point to evaluate the **target** lesions

Target lesion response:

- At baseline and all subsequent tumor assessments, measurable tumor burden is the sum of the longest diameters (SLD) of all **target** lesions
- Complete Response (CR) – disappearance of all measurable lesions
 - Pathologic lymph nodes must have reduction in short axis to < 10 mm
- Partial Response (PR) – decrease of 30% or greater in tumor burden compared with baseline
- Stable Disease (SD) - not meeting the criteria for CR, PR, or progressive disease
- Progressive Disease – increase of 20% or greater in tumor burden compared with nadir, or the appearance of one or more new lesions

Non-target lesion response:

- CR – disappearance of all non-**target** lesions
 - Pathologic lymph nodes must have reduction in short axis to < 10 mm
- SD – persistence of one or more non-**target** lesions, not meeting the criteria for CR or progressive disease
- Progressive disease – unequivocal progression of existing non-**target** lesions, or the appearance of one or more new lesions

Overall response:

- CR
 - Complete disappearance of all lesions
 - Pathologic lymph nodes must have reduction in short axis to < 10 mm
 - Confirmation scan required - repeat, consecutive assessment no less than 4 weeks from the date of the first documented response
 - CR is dated at time of confirmation scan
- PR
 - Decrease in tumor burden $\geq 30\%$ relative to baseline, or
 - Complete disappearance of all **target** lesions with presence of non-**target** lesions
 - Confirmation scan required - repeat, consecutive assessment no less than 4 weeks from the date of the first documented response
 - PR is dated at time of confirmation scan
- SD
 - **Target** lesions not meeting criteria for CR, PR or progressive disease, or
 - In subjects with only non-**target** disease, persistence of one or more non-**target** lesions
- Progressive Disease
 - Radiologic detection of $\geq 20\%$ increase in tumor burden relative to nadir and at least 5 mm absolute increase, or
 - Unequivocal progression of non-**target** lesions, or
 - The presence of new lesions
 - Confirmation scan required - repeat, consecutive assessment 4-6 weeks from the date of the first documented response
 - Radiographic progressive disease is confirmed at repeat imaging (progressive disease on two consecutive scans 4-6 weeks apart) if:
 - Tumor burden remains increased by $\geq 20\%$ and at least 5 mm absolute increase relative to nadir, or
 - Unequivocal progression of non-**target** lesions is observed, or
 - New lesions are present
 - Subjects with a global deterioration of health status requiring discontinuation of treatment prior to radiologic confirmation of disease progression should have the reason for treatment discontinuation classified as 'clinical disease progression' not 'radiographic progressive disease'. Every effort should be made to radiologically confirm progression even after discontinuation of treatment.

Summary of Measurement and Tumor Response Assessment Based on Modified RECIST 1.1	
Measurable lesions	
 Non-nodal lesions: ≥ 10 mm (unidimensional measurement) Pathologic lymph nodes: longest diameter short axis ≥ 15 mm
Measurement of each lesion	
 Non-nodal lesions: The longest diameter (mm) in the axial plane Pathologic lymph nodes: short axis (mm)
Tumor burden	
 Sum of the longest diameters (SLD) of all target lesions Up to 5 lesions per organ, up to 10 total
Response assessment: target lesions (calculated from % change in tumor burden)	
 CR: Disappearance of all lesions 
 Pathologic lymph nodes short axis < 10 mm PR: $\geq 30\%$ decrease from baseline SD: Does not meet criteria for CR, PR or progressive disease. Progressive disease: $\geq 20\%$ increase (and ≥ 5 mm absolute increase) from nadir
Response assessment: non- target lesions	
 CR: Disappearance of all lesions 
 Pathologic lymph nodes short axis < 10 mm SD: Persistence of one or more non-target lesion(s) Progressive disease: Unequivocal progression of existing non-target lesions
New Lesions	The presence of new lesion(s) defines progression
Confirmation	Confirmation by subsequent assessment after ≥ 4 weeks required for CR, PR and progressive disease.

Summary of modified RECIST 1.1 Overall Response Assessment			
Target lesions (tumor burden) ^a , %	Non- target lesions	New lesions	Overall Response using modified RECIST 1.1
↓ 100%	Absent	Absent	CR ^b
None ^d	Absent	Absent	CR ^b
↓ 100%	Present	Absent	PR ^b
↓ $\geq 30\%$	Absent/Present	Absent	PR ^b
↓ $< 30\%$ to ↑ $< 20\%$	Absent/Present	Absent	SD
None ^d	Present	Absent	SD
↑ $\geq 20\%$	Any	Any	Progressive disease ^c
Any	Unequivocal progression	Any	Progressive disease ^c
Any	Any	Present	Progressive disease ^c
NA/ND/UE	Absent/Present	Absent	UE
None ^d	NA/ND/UE	Absent	UE

CR = complete response; NA = not available; ND = not done; PR = partial response; RECIST = Response Evaluation Criteria in Solid Tumors; SD = stable disease; UE = unable to evaluate

^a Decrease assessed relative to baseline. Increase assessed relative to nadir.

^b Response: CR and PR require a confirmation assessment after ≥ 4 weeks, may also wait until the next scheduled imaging

^c Progression: Progressive disease requires a confirmation assessment 4-6 weeks after initial radiographic progressive disease is observed

^d Subjects with non-**target** lesions only

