Cytokine Release Syndrome (continued)					
3	Symptoms require and respond to aggressive intervention 
 • Grade 1 CRS symptoms, AND • Oxygen requirement \geq 40%, OR • Hypotension requiring high-dose^b or multiple vasopressors, OR • Grade 3 organ toxicity or grade 4 transaminitis per CTCAE criteria 	Immediately interrupt / delay AMG 160 until event improves to CRS grade \leq 1.	Admit to intensive care unit for close clinical and vital sign monitoring per institutional guidelines (unless related to asymptomatic elevation of liver enzymes). Administer [REDACTED] (or equivalent) IV at a dose maximum of 3 doses of 8 mg (24 mg/day). The dose should then be reduced step-wise. AND/OR Investigators should also consider use of tocilizumab ^{c,d,e} as an additional therapy in this setting at a dose of 4 - 8 mg/kg IV as a single dose. Persistent tachycardia with complications (eg, atrial fibrillation) should be managed with rate control medications (eg, metoprolol) along with cardiology consultation. [REDACTED]	
 • Re-start possible if successfully managed and improved to \leq grade 1 within 7 days. • Consult Amgen medical monitor. • In case of infusion interruption, continue treatment with next planned dose (do not resume prior infusion). • Delay of next infusion: 
 – < 7 days: administer the delayed infusion (as long as the next scheduled infusion is > 6 days from delayed infusion) and follow the schedule of assessments for the cycle day on which the infusion was originally planned. – > 7 days: skip the infusion and resume schedule of assessments for the next scheduled infusion • Hospitalization: 48 hours • Dose modification: reduce to next lower dose (continuation at same dose with [REDACTED] may be allowed – consult with medical monitor) Additional measures: [REDACTED] and additional assessments as indicated in Section 6.2.2.1.2.4	If there is no improvement to CRS \leq grade 1 within 7 days. OR If subject missed more than 2 consecutive doses of AMG 160 Decision to discontinue should be made in consultation with Amgen medical monitor.

Abbreviations and footnotes defined on last page of table.

Table 6-3. Infusion Interruptions/Delays/Withholding/Permanent Discontinuation and Management of Adverse Events Including Dose Reductions

Grade	Description of Severity ^a	Interruption/Delay	Specific Management	Re-start guidance	Permanent Discontinuation

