Cytokine Release Syndrome (continued)					
4	Life-threatening symptoms 
 • Grade 1 CRS symptoms, AND • Requirement for ventilator support OR • Grade 4 organ toxicity (excluding transaminitis) per CTCAE criteria 		Admit to intensive care unit for close clinical and vital sign monitoring per institutional guidelines. Administer [REDACTED] (or equivalent) IV at a dose maximum of 3 doses of 8 mg (24 mg/day). Further corticosteroid use should be discussed with the Amgen medical monitor. Additionally, tocilizumab ^{c,d,e} should be administered if regionally available at a dose of 4 - 8 mg/kg as a single dose and may be repeated once within 24 to 48 hours based on clinical assessment. Persistent tachycardia with complications (eg, atrial fibrillation) should be managed with rate control medications (eg, metoprolol) along with cardiology consultation. [REDACTED]	N/A	Immediately stop the infusion (if applicable) and permanently discontinue AMG 160

Abbreviations and footnotes defined on last page of table.

Table 6-3. Infusion Interruptions/Delays/Withholding/Permanent Discontinuation and Management of Adverse Events Including Dose Reductions

Grade	Interruption/Delay	Specific Management	Re-start guidance	Permanent Discontinuation
Tumor Lysis Syndrome (TLS) – Grading according to Cairo-Bishop Criteria				
2 (clinical TLS)	Immediate interruption/ delay until event has improved to grade ≤ 1	TLS should be managed according to the local standard of care and institutional guidelines.	
 • Re-start possible if successfully managed and improvement to \leq grade 1 in ≤ 14 days • Consult Amgen medical monitor. • In case of infusion interruption, continue treatment with next schedule infusion (do not resume prior infusion). • Delay of next infusion: 
 – < 7 days: administer the delayed infusion (as long as the next scheduled infusion is > 6 days from delayed infusion) and follow the schedule of assessments for the cycle day on which the infusion was originally planned. – > 7 days: skip the infusion and resume schedule of assessments for the next scheduled infusion • Hospitalization: 48 hours • Dose modification: reduce to next lower dose • Additional measures: [REDACTED] and additional assessments as indicated in Section 6.2.2.1.2.4 	
If subject missed more than 2 consecutive doses of AMG 160
 
OR
 
In case of repeat grade 2 TLS event despite dose reduction.

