^b High dose vasopressors (all doses are required for ≥ 3 hours): Norepinephrine monotherapy ≥ 20 µg/min; Dopamine monotherapy ≥ 10 µg/kg/min, Phenylephrine monotherapy ≥ 200 µg/min, Epinephrine monotherapy ≥ 10 µg/min; If on vasopressin, vasopressin + norepinephrine equivalent of ≥ 10 µg/min; If on combination vasopressors (not vasopressin), norepinephrine equivalent of ≥ 20 µg/min

- ^c All sites will ensure that CRS rescue medications are available on-site, including corticosteroids and (for sites in regions where tocilizumab is approved and available, eg, the US and Germany) 2 doses of tocilizumab per study subject
- ^d If tocilizumab is not available, siltuximab (an anti-IL-6 monoclonal antibody) may be used in the management of cytokine release syndrome, following the criteria outlined in the Management of Adverse Events table. The recommended dose of siltuximab is 11 mg/kg administered over 1 hour as an intravenous infusion, consistent with the prescribing information for the treatment of multicentric Castleman's disease (Sylvant Prescribing Information), and the CARTOX Working Group Guidelines for CRS management (Neelapu, 2018). Siltuximab may be repeated if needed, in the event that CRS recurs after a subsequent infusion of AMG 160. Siltuximab may not be repeated in an individual subject that develops anaphylaxis to siltuximab, or gastrointestinal perforation after siltuximab.
- ^e A subgroup analysis for subjects treated with siltuximab will be evaluated, including CRS outcomes, safety, and PK data.

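### Tocilizumab repeat instructions conflict between Table 6-3 and Table 11-7 for subjects with grade 3 or higher CRS with hypotension and concurrent ICANS, and the two-dose stock matches only Table 6-3

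*Protocol*

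**What the plan says.** **Protocol Section 6.2.2.1.2, Table 6-3, CRS rows.** For grade 3 CRS, investigators should consider tocilizumab "as an additional therapy in this setting at a dose of 4 - 8 mg/kg IV as a single dose". For grade 4 CRS, tocilizumab at 4-8 mg/kg should be given where regionally available, "as a single dose and may be repeated once within 24 to 48 hours based on clinical assessment".

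**Table 6-3, neurological events row (grade 2 or higher).** CRS-related neurological events are sent to the ICANS grading and management system. Tocilizumab is mentioned there for events associated with CRS, and footnote c is attached.

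**Table 6-3, footnotes c and d.** In regions where tocilizumab is approved and available, sites must hold "2 doses of tocilizumab per study subject". If it is not available, siltuximab may be used.

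**Section 11.10.1.** For the grading and management of CRS, the reader is referred to the main protocol body.

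**Section 11.10.3, Table 11-7, concurrent-CRS column.** At ICANS grade 1 the trigger is grade 3 or higher "CRS with hypotension, tocilizumab" at 8 mg/kg, not above 800 mg per dose. ICANS grades 2 to 4 repeat the instruction: "Anti-IL-6 therapy as per grade 1". Footnote d allows repeats every 8 hours as needed, if there is no response to IV fluids or increasing supplemental oxygen, and sets the ceiling: "Limit to a maximum of 3 doses in a 24-hour period; maximum total of 4 doses".

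**The concern.** Tables 6-3 and 11-7 do not cover separate patients. The tocilizumab trigger in Table 11-7 is itself a CRS grade of 3 or higher, so every subject who meets it also sits in a grade 3 or grade 4 CRS row of Table 6-3. The overlap is foreseeable: Table 2-1 lists neurologic signs among those of CRS and says that neurologic toxicities are seen mainly with CRS.

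What is at stake is rescue treatment for CRS, listed as an identified risk in Table 2-1. Two sites following the same protocol could treat the same event with different numbers of doses at different intervals, and each could cite a table. The stock rule was evidently sized to one of the two. Supply is a practical matter here, since the Amendment 3 summary gives site shortages of tocilizumab as its reason.

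**Working it through.** No sample size, boundary or error rate is involved. The check is a dose count from the visible text.

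**Step 1. Reproduce the 24-hour limit in Table 11-7 footnote d.** One dose every 8 hours gives 24 / 8 = 3 doses in 24 hours (at 0, 8 and 16 hours). This matches the stated 3. The total of 4 is a stated limit and cannot be derived.

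**Step 2. Set the instructions side by side.**

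| | Table 6-3, CRS grade 3 | Table 6-3, CRS grade 4 | Table 11-7, CRS grade 3 or higher with hypotension plus any ICANS grade |
|---|---|---|---|
| Amount per dose | 4-8 mg/kg | 4-8 mg/kg | 8 mg/kg, at most 800 mg |
| Repeat | none stated | once, within 24 to 48 h | every 8 h as needed |
| Doses in first 24 h | 1 | 1 (2 on a loose reading of the window) | up to 3 |
| Total doses | 1 | up to 2 | up to 4 |

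- Ratio of totals: 4 / 1 = 4-fold for grade 3 CRS and 4 / 2 = 2-fold for grade 4 CRS.
- Largest cumulative amount: 1 x 8 = 8 mg/kg (grade 3) or 2 x 8 = 16 mg/kg (grade 4) under Table 6-3, against 4 x 8 = 32 mg/kg under Table 11-7 before the 800 mg cap.
- The amounts per dose are not in themselves incompatible: 8 mg/kg lies within 4-8 mg/kg, and the cap binds only above 800 / 8 = 100 kg. The conflict lies in the repeats.

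**Step 3. Look for a precedence rule.** The neurological row of Table 6-3 points to the ICANS system, but it covers events of grade 2 or higher. Table 11-7 already gives tocilizumab at ICANS grade 1, which that row does not reach. Section 11.10.1 points the other way, sending CRS management back to the main body. Table 11-7 labels its column as additional therapy in concurrent CRS and does not switch off the CRS rows. No visible sentence ranks the two tables.

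**Step 4. Compare with the stock (2 doses per subject).**

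- Against Table 6-3: 2 - 2 = 0, an exact match with its grade 4 maximum.
- Against Table 11-7 in 24 hours: 3 - 2 = 1 dose short.
- Against Table 11-7 in total: 4 - 2 = 2 doses short.
- At 8-hour intervals, two doses are used at 0 and 8 hours, so one subject's required stock is gone before the dose permitted at 16 hours.

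**The case against.** The strongest reply is that a routing rule exists. Table 6-3 itself sends CRS-related neurological events to the ICANS guidance, and Table 11-7 is the specific provision for the combined case. This narrows the point, because the two tables are linked. It does not settle it: the link omits ICANS grade 1, does not say that it replaces the CRS rows, and is countered by Section 11.10.1. If the link does govern, the stock rule attached to that same row is 2 doses below the permitted total.

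Second, the grade 3 CRS text is advisory. It describes a single dose without forbidding another, and the Table 11-7 repeats are conditional. This stands in part: the 1 for grade 3 is the number stated, not an express cap. The firmest comparison is at grade 4, where one repeat at 24 to 48 hours meets a repeat every 8 hours.

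Third, the management cells for CRS grades 3 and 4 each end in redacted text, which might hold a cross-reference. That cannot be excluded, so the finding is confined to what is visible.

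Fourth, a reader might infer from the stock rule that a site could not supply the Table 11-7 maximum. The documents do not support that. The 2 doses are an availability requirement per subject and not a cap on use; nothing says that one subject's doses are reserved; the rule is limited to certain regions; and siltuximab is the written fallback.

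**Conclusion.** The point holds for one subset: grade 3 or higher CRS with hypotension and concurrent ICANS of any grade. For that subject the visible text gives totals of 1 or 2 doses against up to 4, and a repeat interval of none or 24 to 48 hours against 8 hours. The stock falls short of the larger maximum by 1 dose in 24 hours and 2 in total. That is a shortfall against a permitted maximum and not an impossibility. The conclusion assumes that the redacted cells contain no precedence rule.

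Two wider readings are tempting and should not be drawn. One is that the conflict covers all grade 3 or higher CRS with neurotoxicity; Table 11-7 gives tocilizumab only where there is hypotension. The other is that it distorts the siltuximab monitoring rule (Protocol Section 9.4.1.1.1, SAP Section 7.1.1) by deciding who enters its denominator. That rule counts subjects actually treated with siltuximab, for whatever reason, and the documents give no frequency of subjects needing a further tocilizumab dose from which an effect could be computed. No statistical figure in either document changes.

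This should be corrected because it concerns rescue treatment. No view is taken here on which limit is right.

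**What to change.** Reconcile the CRS grade 3, CRS grade 4 and neurological rows of Table 6-3, its footnote c, Section 11.10.1, and Table 11-7 with its footnote d. State in one place which table governs tocilizumab amount, repeat interval and maximum when CRS and ICANS coincide, and cover ICANS grade 1 explicitly. Then align the footnote c stock requirement with the chosen rule. The clinical team sets the limits.

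The cost is protocol wording and possibly more tocilizumab held at sites. No analysis, boundary or sample size needs to be redone.
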